8.1.2 Initial Procedure Visit(s) (Baseline)

[Purpose]: To perform surgical procedures aimed at removing devitalized tissue

The Initial Procedure Visit may occur after all screening eligibility criteria have been confirmed. It may occur on the same day as screening, but must occur within (7) seven days of the Screening Visit. All subjects will undergo standard aggressive therapy consisting of surgical sharp debridement in the OR, resection of necrotic bone, bone biopsy for microbiology and histopathology, and wound lavage. It is advised to bring the TTAX01 product to the OR if it is expected that the surgical procedures can be completed without staging, in case the subject is randomized to that treatment group. Randomization will take place if primary closure is not possible and further surgery is not needed.

- Perform surgical sharp debridement in the OR, to remove:
 - infectious agents and biofilms (purulence),

- all debris, eschar, callus and macerated non-viable tissue from the wound base, and
- Dead (suprabasal epidermis), scarred (elevated/edematous) and necrotic/macerated tissue from the wound edge.
- Resect necrotic bone. Surgical Resection will be performed to remove as much of the necrotic bone detected by the radiographic evidence as is appropriate.
 - If the Investigator notes the following: (1) severe clinical signs of infection, (2) acute lymphangitis, or (3) the wound severity requires a subsequent surgical procedure to remove any remaining non-viable or unhealthy tissue, the surgical procedure should be staged, and randomization will be held until the final staged procedure.
 - In this instance, the interval between the Initial Procedure Visit and subsequent final staged procedure should be ≤ 14 days.
 - During this period, the wound bed should be managed with SC alone and no prohibited treatments should be used as detailed in Section describing Concomitant Therapy.
- Obtain bone biopsies for microbiology and histopathology. A biopsy to obtain specimens from the (a) resected bone containing suspected osteomyelitis (labeled 'dirty bone') and the (b) clean margin (labeled 'clean bone') will be submitted to the local laboratory for microbiology (culture and sensitivity) and histopathology examination.
- At the same time, obtain tissue harboring suspected infection and send for microbiology (culture and sensitivity).
- Perform wound lavage using sterile saline solution with or without antibiotics.
- If the wound can be closed by primary intention at this point, proceed to do so and the subject will exit the study as a Screen Failure.

Otherwise,

 Obtain post-debridement photograph and measurement of the surface area and volume of the index ulcer using the provided electronic wound imaging and measuring device.
 This is needed for randomization. Proceed with Randomization (refer to Section 8.1.3), unless a staged procedure is necessary, in which case do not randomize. Instead, provide the subject with appropriate wound dressing and off-loading and schedule them to return for completion of this Initial Procedure.

8.1.3 Randomization

[Purpose]: To randomly assign eligible subjects to a treatment group, with stratification, and initiate therapy.

Obtain the treatment group assignment using the computer-based randomization tool.

TREATMENT GROUP ONLY:

- Apply TTAX01 deep below the surface of the surrounding skin to cover and be in contact with the exposed tissue at the base of the wound, rough side down, and surgically fixed by sutures or staples. TTAX01 must be fenestrated prior to applying the secondary dressing. The initial application will occur as part of the surgical procedure.
 - Multiple pieces of TTAX01 may be used if required to cover the entire wound bed.
 - Obtain post-application photograph of TTAX01 using the provided electronic wound imaging and measuring device

ALL SUBJECTS (BOTH GROUPS):

- Apply wound dressing including a non-adherent, standard foam pad or alginate dressing (e.g., hydrogels, foam dressings, and alginates) that is appropriate for the amount of drainage, and a secondary bandage to ensure a moist wound environment, which adequately controls exudate and avoids maceration of the surrounding skin.
- Continue, adjust, or initiate an appropriate systemic antibiotic regimen. Topical antibiotics should not be administered. A definitive therapy will be guided by the microbiological results based on bone biopsy. An Infectious Diseases specialist may be

consulted to determine the appropriate antibiotic regimen to proceed with if the pathology report confirms the 'clean margin' is free of osteomyelitis. At least six (6) weeks of systemic antibiotic therapy is required in this protocol. If the initially chosen antibiotic is changed based on culture and sensitivity results, the total length of all antibiotic treatment will remain at 6 weeks.

Provide an off-loading device appropriate to the location of the wound with full length boot or total contact cast (unless not appropriate, where a substitute off-loading device can be made per the physician's suggestion with sponsor approval) with off-loading instructions. The substituted choice of off-loading modality should be based on the wound's location, the presence of any associated peripheral artery disease, the presence and severity of infection, and the physical characteristics of the subject.

Schedule the next Treatment Period Visit in one week $(7 \pm 2 \text{ days})$.

8.1.4 Treatment Period (Visits 2– 16; 7 ± 2 days)

[Purpose]: To monitor safety and wound healing, adjust antibiotic regimens, and administer treatment. At each visit of Visits 2 through 16, the listed procedures will be performed for the subject based upon status of the wound.

If the subject will discontinue from TTAX01 treatment at any of these visits, the subject should continue with the scheduled visits through the end of the study in order to observe wound status and general safety. If the subject will discontinue from the trial (drop-out), move immediately to the End of Study Visit (Visit 29) and complete all of the procedures listed.

Beginning at Visit 9 (Day 57), if the wound is not \geq 50% reduced in wound area versus the post debridement measurement obtained at the Initial Procedure Visit prior to randomization, the Investigator may begin to utilize adjunctive therapies as explained in Section 6.5.

If at any Treatment Visit the index ulcer is observed to be closed, perform the following procedures:

- Assess adverse events
- Review concomitant medications
- Assess subject compliance regarding off-loading since the last visit
- Obtain photographs of the closed ulcer using the electronic wound imaging and measuring device
- Observe the wound if it is fully epithelialized with no drainage or need for a dressing, record it as closed.

The next visit scheduled will serve as the first consecutive confirmation visit in 14 ± 2 days and will begin the confirmation of closure procedures (refer to Section 8.1.9).

If the wound remains open, conduct the following procedures:

- Assess adverse events
- Review concomitant medications. These will be recorded in the subject's source document, but should only be recorded in the eCRF for the following:
 - All current and past treatments for the index ulcer only
 - Concomitant medications used to treat the index ulcer (e.g., systemic antibiotics for an index ulcer infection) and the peri-ulcer area (such as treatment for erythema, irritation, itching), together with the indication for the medication
 - Concomitant medications used to treat all SAE, and all AE considered "RELATED" to the product will be recorded in the appropriate eCRF.
- Assess subject compliance regarding off-loading since the last visit
- Assess the foot and lower extremity, then assess the index ulcer after removal of the dressing (but do not remove residual TTAX01 in the treatment group).
 - Determine whether skin and soft tissue infection (SSTI) is present. If not, follow the scheme shown in *Figure 12.1-1* (Appendix)
 - If SSTI is present, without evidence of osteomyelitis, follow the scheme shown in *Figure 12.1-2* (Appendix); withhold TTAX01 application, obtain a deep tissue biopsy for histopathology, culture and sensitivity, and adjust the antibiotic regimen

- (start a 2 week course of antibiotics if none are being taken, or revise antibiotics if still being taken for a previous infection)
- If new, recurrent or persistent osteomyelitis is suspected, follow the scheme shown in *Figure 12.1-3* (Appendix); repeat procedures to diagnose osteomyelitis (PTB plus imaging or scanning). If osteomyelitis is confirmed, follow the procedures for the Initial Procedure Visit, including application of TTAX01 (start a 6 week course of antibiotics if none are being taken, or revise antibiotics if still being taken for a previous osteomyelitis).
- Clean the wound using sterile saline, non-ionic cleanser or a hypochlorous solution.
 Antiseptic agents including hydrogen peroxide, acetic acid, chlorhexidine, povidone/iodine, and cetrimide should not be used.
- The wound should be sharply debrided to remove callus, macerated, necrotic/devitalized/non-viable tissue and purulence observed on the wound edge and wound bed. Debride until the wound edge is clean and sharply defined, with at least punctate bleeding at the edge and wound bed.
- Obtain photograph and measure the area and volume of the wound using the provided electronic wound imaging and measuring device (after debridement, if performed).
- Determine if additional TTAX01 is necessary **only for subjects in the treatment group** who have not achieved closure.
 - Remove any visible sutures or staples from prior treatment.
 - Remnant TTAX01, if present in the ulcer bed following debridement, should be left in place beneath reapplication.
 - TTAX01 may be reapplied following sharp debridement, for the index ulcer displaying the following criteria:
 - When there is no TTAX01 remnant detected one week after each application, suggesting dislodgement.
 - At least four (4) weeks from previous application of TTAX01 under the following conditions:

- o Neither SSTI or osteomyelitis are observed, and
- Wound healing has stalled, defined as no change of the wound surface area compared to the wound surface area at last application, or
- Wound base does not exhibit hyperemic granulation tissue, or
- o Wound edge is edematous and elevated.
- TTAX01 should be secured in place by sutures or staples.
- TTAX01 must be fenestrated.
- Obtain post-application photograph of TTAX01 using the electronic wound imaging and measuring device
- TTAX01 will be withheld for 3 weeks following each application, and withheld if the wound shows any of the following favorable signs of healing:
 - Presence of TTAX01 tissue remnant
 - Wound base covered by a black or yellow cap/eschar
 - Wound base showing hyperemic granulation tissue
 - Wound showing epithelialization.
- Apply wound dressing including a non-adherent, standard foam pad or alginate dressing
 (e.g., hydrogels, foam dressings, and alginates) that is appropriate for the amount of
 drainage, and a secondary bandage to ensure a moist wound environment, which
 adequately controls exudate and avoids maceration of the surrounding skin.
- Continue with the off-loading device appropriate to the location of the ulcer (preferably with full length boot or total contact cast, unless not appropriate per the physician, in which case a substitute off-loading device can be made with sponsor approval)
- Adjust infection management including antibiotics as needed, as indicated by the results from the microbiology and histopathology bone biopsy.

Schedule the next Treatment Period visit in one week $(7 \pm 2 \text{ days})$ or, if the subject is at Visit 16, schedule the first Weekly Observation Period Visit 17 in one week $(7 \pm 2 \text{ days})$.

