5.3 Lifestyle Considerations

Subjects are expected to maintain ongoing care and management of their diabetes under the supervision of a qualified diabetologist, endocrinologist or internist with appropriate specialty training and experience. The need for off-loading of the wound requires compliance with daily wearing of the off-loading device, which may limit ambulation to some degree.

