7.2 Participant Discontinuation / Withdrawal from the Study

All subjects have the right to discontinue their participation in the trial at any time. The Investigator may also withdraw a subject from the trial at any time if they deem it medically necessary. The reason for discontinuation should be documented and trial staff should attempt

to bring the subject in for an Early Termination Visit and perform all applicable assessments, as appropriate, listed under the End of Study Visit for discontinuations that occur during the Trial Period.

Subjects may be discontinued from the trial for the following reasons:

- Adverse Event (including illness)
- Subject withdrawal of consent
- The Sponsor or Investigator terminates the trial
- Lost to follow-up
- Product-related > Grade 2 skin or systemic allergic reaction (CTCAE criteria)
- Ulcer-related complications (i.e., life-threatening, infection-related sepsis complications)
- Limb amputation (i.e., full amputation involving the index ulcer anatomic location)

In the event of a subject's withdrawal, the Investigator will promptly notify the medical monitor and will make every effort to complete all procedures at the End of Study Visit. Even if removed subjects have been removed from the trial or if an adverse event remains ongoing, Investigators should follow up with subjects as per their standard medical practice.

Discontinued subjects will not be replaced. Simultaneous screening at multiple sites may result in an allowable modest over-enrollment.

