8.1.8 End of Study Visit (Visit 29; Day 344 ± 7)

[Purpose]: To document the patient status if they complete the entire treatment period or if they are withdrawn from the study during this period.

Begin with the following procedures:

- Assess adverse events
- Review any changes in concomitant medications
- Obtain photograph of the index ulcer using the electronic wound imaging and measuring device
- Assess the index ulcer

If at this visit a previously unhealed index ulcer is observed to be closed,

perform the following procedures:

- Assess adverse events
- Review concomitant medications
- Assess subject compliance regarding off-loading since the last visit
- Obtain photographs of the closed ulcer using the electronic wound imaging and measuring device

 Observe the wound – if it is fully epithelialized with no drainage or need for a dressing, record it as closed.

The next visit scheduled will serve as the first consecutive confirmation visit in 14 ± 2 days and will begin the confirmation of closure procedures (refer to Section 8.1.9).

Otherwise,

- Perform physical examination, including vital signs (i.e., heart and respiratory rates, blood pressure, and temperature while patient is seated)
- Perform Laboratory Assessments as listed in Table 8.1.1-1 including the pregnancy test for females of childbearing potential
- Instruct subject to complete the PROMIS Lower Extremity Function questionnaire and the CWIS.

Complete subject disposition forms and exit the subject from the study.

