8.1.11 Early Termination Visit

If a subject is withdrawn from their randomized treatment for any reason, they should be encouraged to continue with the subsequent scheduled visits for observation. The Observational Period visits are particularly valuable in monitoring long-term adverse events, (e.g., unresolved ongoing adverse events, and new treatment related adverse events including limb amputation for ulcers that do not heal).

If a subject is being withdrawn from the trial, attempt to schedule an early termination visit at which the End of Study procedures are carried out (refer to Section 8.1.6). Complete procedures described therein and document the reason for the subject's withdrawal.

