9.4.3 Analysis of the Secondary Endpoints

Secondary efficacy endpoints in this study include proportions of index ulcer healed by Week 50, proportions of wound re-ulcerations by Week 50, proportions of minor and major amputations by Week 50, and total score of PROMIS Lower Extremity Function Questionnaire at end of study.

The non-parametric Cochran-Mantel-Haenszel (CMH) test with adjustment for baseline wound size cohort will be used to examine treatment effects for the SC plus TTAX01 arm vs. SC alone arm on proportion of subjects with index ulcer achieving and remaining healed at Week 50, proportion of subjects (among those with complete wound healing before Week 50) with wound re-ulceration at Week 50, and proportion of subjects with minor and/or major amputations by Week 50. Subjects' missing values at Week 50 in these endpoints, due to either no assessment or early termination from the study, will be imputed using the last-observation carry forward (LOCF).

An analysis of covariance model (ANCOVA) with treatment and baseline wound size as effect will be used to analyze total score of PROMIS Lower Extremity Function Questionnaire at end of study. Subjects' missing values in this endpoint, due to either no assessment or early termination from the study, will utilize the assessment collected at the early termination visit.

The analyses of the secondary efficacy endpoints will be performed for the ITT population and PP population as well as the LO population.

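### Section 9.4.3 analyses a drop-out's exit PROMIS score as the end-of-study score whenever it was taken, and Section 8.1.11 points sites to a visit list that has no PROMIS

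*Protocol*

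**What the plan says.** Protocol Section 3 makes the PROMIS lower-extremity total score at study end a secondary efficacy endpoint. Section 9.1 gives it a hypothesis, and 9.3 assigns the secondary efficacy analyses to the ITT population.

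- **When it is measured.** The Schedule of Activities (1.3) shows PROMIS at Screening and at End of Study only. The instruction at the final visit is "Instruct subject to complete the PROMIS Lower Extremity Function questionnaire and the CWIS", under the heading "8.1.8 End of Study Visit (Visit 29; Day 344 ± 7" days.
- **What drop-outs do.** Section 8.1.4 tells a subject leaving the trial during Visits 2–16 to "move immediately to the End of Study Visit (Visit 29) and complete all of the procedures listed". For withdrawals in general, 7.2 asks staff to "perform all applicable assessments, as appropriate, listed under the End of Study Visit", and 8.1.11 says to "attempt to schedule an early termination visit at which the End of Study procedures are carried out (refer to Section 8.1.6").
- **How it is analysed.** Section 9.4.3 uses an ANCOVA with treatment and baseline wound size. Where the score is missing, through no assessment or early termination, the analysis "will utilize the assessment collected at the early termination visit". No limit is set on how early that assessment may be.

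**The concern.** The endpoint is function at about Week 50. The substitution rule lets a score from any time after randomization stand in for it. An early exit score is taken soon after surgical debridement and bone resection. One that follows an amputation, an ulcer complication or another adverse event (all listed in 7.2 as reasons for discontinuation) is taken close to that event. Neither need reflect the same subject's function at Week 50, and the model contains neither the time of assessment nor the screening PROMIS score.

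The trial is open label, and the protocol's own hypotheses expect fewer amputations with TTAX01. Drop-out that differs by arm in rate, timing or reason is therefore plausible. The estimated mobility difference would then partly reflect who left and when. If drop-out is balanced, the early scores pull a real Week 50 effect towards zero.

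The cross-reference in 8.1.11 is a separate defect. Section 8.1.6 is the Bi-Weekly Observation list, which contains no PROMIS, CWIS or laboratory tests. The End of Study list is in 8.1.8. A site that follows the reference literally would not collect the score that 9.4.3 relies on.

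**Working it through.** **The plan's own figures.** There is none to reproduce for PROMIS: no SD, effect size, power or drop-out by arm is given. Section 9.2 sizes the primary endpoint only, but supplies two usable inputs: 110 + 15 = 125 subjects per arm, and 10% drop-out overall.

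**Timing.** Section 8.1.4 sets Visit 9 at Day 57, with weekly visits.
- Visit 2: 57 − 7×7 = Day 8. Visit 16: 57 + 7×7 = Day 106.
- Gap to Day 344: 344 − 106 = 238 days (34 weeks), up to 344 − 8 = 336 days (48 weeks).

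**Scale.** Section 12.2 lists 8 + 4 + 7 = 19 items scored 1–5, so the total runs from 19 to 95. Higher is better.

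**Bias with no true effect.** Let the exit score lie *d* points below the Week 50 score it replaces, and let drop-out be p_T (TTAX01) and p_C (control). Then

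bias (TTAX01 − control) = d × (p_C − p_T).

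The sign follows the arm that loses more subjects. More control drop-out favours TTAX01, and more TTAX01 drop-out works against it. With equal rates and equal deficits the bias is 0.

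Assumptions, none of them from the protocol: SD 18; *d* from 5 to 20; drop-out differing by 5 or 10 percentage points; every drop-out supplies an exit score.

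SE = 18 × √(2/125) = 2.28.

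The two-sided error is 1 − Φ(1.96 − b/SE) + Φ(−1.96 − b/SE), where b is the size of the bias:

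| Drop-out difference | d | Bias (points) | Two-sided error at nominal 5% |
|---|---|---|---|
| 5 points | 5 | 0.25 | 5.1% |
| 5 points | 10 | 0.50 | 5.6% |
| 5 points | 20 | 1.00 | 7.2% |
| 10 points | 5 | 0.50 | 5.6% |
| 10 points | 10 | 1.00 | 7.2% |
| 10 points | 20 | 2.00 | 14.2% |

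**Dilution with a true effect.** Take a true Week 50 difference of 5 points and no difference yet at exit. The estimate is (1 − p_T) × 5 + d × (p_C − p_T).
- 10% in both arms: 0.90 × 5 = 4.5.
- 5% TTAX01, 15% control: 4.75 + 0.10d, which is 5.25 at d = 5 and 6.25 at d = 15.
- 15% TTAX01, 5% control: 4.25 − 0.10d, which is 3.75 at d = 5 and 2.75 at d = 15.

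**Where the rule gives no value.** Attendance at the exit visit is only attempted (7.2, 8.1.11). Section 9.4.3 also covers subjects with no assessment, but a completer who missed the questionnaire has no early-termination visit. Neither that completer nor a drop-out who never attends has a score to substitute.

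**The case against.** **Few early drop-outs.** Section 3 expects few drop-outs in the first 26 weeks and possibly more later. Later exits lie closer to Week 50, where a deficit of 10 to 20 points is hard to defend. Some drop-outs will give no exit score. This stands, and it moves the plausible bias towards the lower end of the table.

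**Other analyses exist.** Section 9.4.3 repeats the secondary analyses in the PP and LO populations, and 9.4.1 leaves missing-data detail and sensitivity analyses to the SAP, which is not at hand. True, but 9.4.3 itself fixes the substitution. The LO and PP sets are also selected after randomization, so neither replaces the ITT comparison.

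**Off-loading.** A reader might infer that early scores are low because those subjects wear a boot or cast, "which may limit ambulation to some degree", while Week 50 scores are free of this. The documents do not support so clean a contrast: off-loading continues through Visits 24–28 (1.3, 8.1.7). Time since surgery and wound status are the firmer differences.

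**Filing under Visit 29.** A reader might also infer from 8.1.4 that early CWIS and laboratory values enter the end-of-study tables as Day 344 data. No eCRF is shown, nothing says that the exit date is lost, and 9.4.4 leaves missing safety values missing. Sections 7.2, 8.1.11 and 9.4.3 already name a separate early termination visit.

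**The wrong reference.** Section 8.1.11 still names the End of Study procedures, and 7.2 and 8.1.4 point to the right visit. That sites would collect nothing is the worst case, not the likely one.

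**Conclusion.** The point holds for one secondary endpoint. As written, 9.4.3 treats a PROMIS score from any time after randomization as an end-of-study score in the ITT analysis, with no adjustment for timing. The 8.1.11 cross-reference is wrong.

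The consequence is bias of either sign if drop-out differs by arm in rate, timing or reason, and dilution of a true Week 50 effect if it does not. The illustrated bias of 0.25 to 2 points against a standard error of 2.28 rests on an assumed SD, exit deficit and drop-out split. It shows a range, not a forecast, and the upper end needs both large deficits and a wide drop-out difference. It would be too strong to say that the rule favours TTAX01 or produces a false positive: the protocol gives no drop-out by arm, and balanced drop-out with equal exit deficits leaves the null comparison unbiased. The primary endpoint is not affected. The change is worth making because it is cheap.

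**What to change.** 1. **Section 8.1.11:** change the reference from 8.1.6 to 8.1.8, so that PROMIS, CWIS and laboratory tests are collected at exit.
2. **Section 8.1.4:** call the drop-out assessment the Early Termination Visit, as 7.2, 8.1.11 and 9.4.3 already do, and keep its actual study day.
3. **Section 9.4.3:** make the main PROMIS analysis a multiple imputation of the Week 50 score by arm, from variables that completers also have: screening PROMIS, wound size, and healing and amputation status. Do not use exit PROMIS or exit day as predictors. No subject has both an exit score and a Week 50 score, so their relation cannot be estimated from these data. Keep exit-score substitution as a sensitivity analysis.

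The cost is protocol and SAP wording and a little more analysis work, with no new subjects or assessments. The PROMIS confidence interval may be slightly wider. The imputation assumes that, given those variables, drop-outs resemble completers in the same arm, which is a further reason to keep the sensitivity analysis.

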8.1.9 Confirmation of Closure ("C" Visits)

[Purpose:] These visits serve to confirm that a wound has achieved complete closure

Confirmation of Closure visits are used to record the initial observation of closure, and persistent closure. Ideally, a wound that shows initial closure will still be closed at a confirmation visit two weeks later, and at a second confirmation visit four weeks later. At each of the confirmatory visits, use the Confirmation of Closure visit form(s) to record observations. Continue with the off-loading device appropriate to the location of the ulcer during the period of confirmatory visits.

Perform the following procedures:

- Assess adverse events
- Review concomitant medications
- Assess subject compliance regarding off-loading since the last visit

- Obtain photographs of the ulcer using the electronic wound imaging and measuring device
- Observe the wound if it is fully epithelialized with no drainage or need for a dressing, record it as closed.

If the wound is found to be open at either confirmation visit or if the subject misses a scheduled confirmation visit, record it as such and then move directly to the original schedule of visits. This may become a treatment visit for example if the subject has not passed Visit 16, or an observation visit if the subject has passed Visit 16.

If the index ulcer is closed at the first confirmation visit, schedule the subject to return for a second consecutive confirmation visit in 14 ± 2 days. If the index ulcer remains closed at the second confirmation visit, schedule the subject to begin the Long Term Observation Period at the next study day that will put the subject onto the planned 28 day schedule of visits. For example, if a subject completes the second confirmation visit on Day 50, they should return on Day 64 and continue thereafter with visits every 28 ± 3 days. Days 92, 120, 148, 176, 204, or 232 are the other days on which these subjects can enter into Long Term Observation. Note that Day 176 has a unique window of plus or minus 2 days, otherwise these visits have windows of plus or minus 3 days.

If the initial closure is observed at Visit 28 or 29, the subject should move immediately to the End of Study procedures once both confirmation visits are completed, or if the wound is found to be open at either of the two confirmatory visits.

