8.3 Safety and Other Assessments

Safety is evaluated at each visit by examination of the lower extremity and through both spontaneous and elicited reporting of adverse events.

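### Section 8.3 has the lower extremity examined at every visit, but the lists for the first-closure visit and both confirmation visits omit it, so scheduled limb examination depends on healing

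*Protocol*

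**What the plan says.** Section 8.3 sets a general rule: "Safety is evaluated at each visit by examination of the lower extremity and through both spontaneous and elicited reporting of adverse events".

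Section 8.1.4 ties the procedures done at Visits 2 to 16 to the status of the wound and gives two lists. The first begins "If at any Treatment Visit the index ulcer is observed to be closed". It has five steps: adverse events, concomitant medications, off-loading compliance, photographs, and inspection of the wound ("if it is fully epithelialized with no drainage or need for a dressing, record it as closed"). The second list, for a wound still open, adds "Assess the foot and lower extremity, then assess the index ulcer after removal of the dressing". Under that line it continues with "Determine whether skin and soft tissue infection (SSTI) is present" and with a branch that begins "If new, recurrent or persistent osteomyelitis is suspected, follow the scheme shown in".

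Sections 8.1.5, 8.1.6 and 8.1.7 repeat the five-step list for a newly closed ulcer. Section 8.1.9 uses the same five steps at both confirmation visits. Its introduction adds "Continue with the off-loading device appropriate to the location of the ulcer during the period of confirmatory visits" but no limb assessment.

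**The concern.** At the visits that establish healing, the general safety rule and the visit lists disagree. A site that follows the list examines the limb when the ulcer is open and does not when it has closed. Closure is the primary outcome and is what the product is meant to change, so the scheduled intensity of safety ascertainment would follow the outcome and, through it, the arm.

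This matters because adverse events are compared by group (Section 3) and events related to the index ulcer are listed (9.4.4). Infection, including osteomyelitis, is named among the events to expect (8.4.3.3), and a lower risk of recurrent osteomyelitis is an anticipated benefit (2.3.2). The trial is open label (6.3), and the risk assessment in 2.3.3 relies on weekly visits for safety.

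**Working it through.** **Lists side by side**

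| Visit list | Foot and lower-extremity assessment | SSTI/osteomyelitis determination |
|---|---|---|
| 8.1.4 (Visits 2-16), open | yes | yes |
| 8.1.4, closed | no | no |
| 8.1.5 (Visits 17-20), open | yes | no |
| 8.1.5, closed | no | no |
| 8.1.6 (Visits 21-23), open | yes | yes |
| 8.1.6, closed | no | no |
| 8.1.7 (Visits 24-28), newly closed | no | no |
| 8.1.7, all others, including already healed | yes | yes |
| 8.1.9, both confirmation visits | no | no |

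The limb column splits by wound status in every period from 8.1.4 to 8.1.7. The infection column does not, because open wounds at Visits 17-20 also lack that step. The Schedule of Activities does not close the gap. It marks wound and adverse-event assessment at confirmation visits but has no limb-examination row, and it places the physical examination only at Screening and End of Study.

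**Visits affected.** The plan gives no figure on this point. The only inputs are the planning healing rates in 9.2 (40% control, 65% TTAX01) and the total of 250 subjects, or 125 per arm. Each confirmed closure uses three visits: first observation and two confirmations.

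- TTAX01: 3 × 0.65 = 1.95 visits per randomized subject; × 125 = 243.75.
- Control: 3 × 0.40 = 1.20 visits per randomized subject; × 125 = 150.
- Difference: 0.75 per subject; × 125 = 93.75, or about 94 visits.

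This assumes one closure episode per healed subject. Closures that fail confirmation, and closures after Week 26, would add to both counts.

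**The protocol's own example.** Section 8.1.9 describes a second confirmation on Day 50 and the next visit on Day 64. Counting back 14 days at a time gives a first confirmation on Day 36 and first closure on Day 22; the last open-wound visit is then Day 15. By the lists, limb examinations fall on Day 15 and Day 64, which is 64 − 15 = 49 days apart. A subject with an open wound is examined every 7 days over the same span. If the examination were also done on Days 22, 36 and 50, the longest interval would be 14 days.

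**How much of the between-arm gap comes from the omission.** This is an illustration only. It assumes exponential healing to 40% and 65% by Visit 23 (25 weeks after Day 1), no dropout and no re-opening. With λ = −ln(1 − p)/25, the chance that closure is first seen at week w is exp(−λ × previous visit week) − exp(−λw). Open-wound visits are at weeks 1-19, 21, 23 and 25. Healed subjects resume examinations at the first of weeks 9, 13, 17, 21 or 25 that falls after the second confirmation.

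- As listed, mean limb examinations through Visit 23 are 15.8 (TTAX01) and 18.5 (control), a gap of 2.7.
- With the examination added at the three closure visits, they are 17.7 and 19.6, a gap of 1.9.

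The omission therefore explains less than a third of the gap. The rest comes from the sparser visit schedule after closure, which this point does not challenge.

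**The case against.** The best reply is that 8.3 supplements the lists, so the examination is already required at closure visits and the lists merely fail to repeat it. That reading is possible, but 8.1.4 says that the listed procedures are the ones performed according to wound status, and the open-wound list does spell the examination out. Nor does a healed foot appear to have been judged not to need it, because 8.1.7 examines healed subjects again. No reason is given for leaving it out at the three visits in between.

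Several other objections stand and limit the point:

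- Section 8.3 names a limb examination, not an infection determination. A reader might infer that the missing SSTI/osteomyelitis step also breaches 8.3. It does not; it is a mismatch between lists. It is also not uniform by wound status, since open wounds at Visits 17-20 lack the step and neither branch of the End of Study list contains it.
- The closure visits are not without safety assessment. Adverse events are asked about, photographs are taken and drainage must be absent. Section 6.3 describes closure as judged by sight and touch.
- A reader might infer that infection rates are biased in favour of TTAX01. The counts above are visits at planning rates, not missed events. If healing were equal in the two arms, this difference would vanish.
- A reader might infer that wounds are certified as healed over persisting infection. Nothing in the protocol shows that this happens or how often.

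**Conclusion.** The contradiction between 8.3 and the closed-ulcer and confirmation lists is real and should be corrected. Followed as listed, about three visits per healed subject lack a scheduled limb examination: 1.95 versus 1.20 per randomized subject at the 9.2 rates with one closure episode each. This creates a risk of unequal ascertainment of index-limb adverse events between arms. The size of that risk is unknown, and its direction depends on which arm actually heals more. The documents do not support calling it a demonstrated bias. The primary analysis and the sample size are unaffected. Placement of the infection determination is a second, lesser inconsistency among the visit lists.

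**What to change.** Reconcile 8.3 with the closed-ulcer lists in 8.1.4 to 8.1.7 and with the 8.1.9 list, so that the same lower-extremity safety assessment is stated and recorded at every visit whatever the wound status. The wording already exists as the foot and lower-extremity line in the open-wound lists. A matching field on the Confirmation of Closure form would show that it was done.

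Separately, the sponsor should reconcile at which visits the SSTI/osteomyelitis determination applies, including open wounds at Visits 17-20. The 8.1.4 version should not simply be copied across, because it leads into the TTAX01 placement schemes for open wounds. How a positive finding is managed is for the sponsor to decide.

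The cost is one line in each list and an eCRF field. No visit is added and the sample size does not change.
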